## 7.7. Data Analysis

### 7.7.1. Primary Analysis

#### 7.7.1.1. Main analytical approach

Baseline characteristics and outcomes will be described using counts and relative frequencies for categorical variables and means, standard deviations, medians, minimums, maximums, and quartiles 1 and 3 for continuous variables. For event outcomes, incidence rates will be estimated using unadjusted Poisson regression, accounting for person-time since index (i.e., first CAB+RPV LA injection) where appropriate. Additional analytic approaches may also be considered for select time-to-event outcomes (e.g., time to discontinuation) such as estimators that take into account

right-censoring (e.g., Kaplan-Meier estimator) and multivariable models such as logistic regression as applicable.

Analyses will be stratified by BMI (< 30, ≥ 30-40 and ≥40 kg/m^2), age (18-49, 50-64, ≥ 65 years), sex (male, female), race/ethnicity, sex/race, and country at first CAB+RPV LA injections, as sample size allows, to assess characteristics, adherence, persistence, discontinuation, and virologic effectiveness. Other demographic and clinical variables may also be considered for stratification, if relevant.

Additionally, factors such as, age, sex assigned at birth, race, geographic region, BMI, injection drug use (IDU), CD4 count, history of AIDS-defining events, core class in prior regimen and comorbidities associated with CVF will be explored using a logistic regression model.

The number and proportion of participants with history of resistance to INSTI or NNRTI and individual ARTs and the results of any historical resistance testing will be assessed. Similarly number and proportion of participants with discontinuation/CVF will be assessed for resistance testing and specific INSTI and/or NNRTI RAMs will be described. Subsequent regimen after discontinuation/CVF and virologic outcomes will be described.

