## Data Analysis

Baseline characteristics and outcomes will be described using counts and relative frequencies for categorical variables. Continuous variables will be summarized using summary statistics (means, standard deviations, medians, minimums, maximums, and quartiles 1 and 3). For event outcomes assessed at any point during follow-up, incidence rates will be estimated using unadjusted Poisson regression, accounting for person-time since index (i.e., first CAB+RPV LA injection) where appropriate. Additional analytic approaches may also be considered (e.g., Kaplan-Meier estimator/curve) and multivariable models such as logistic regression as applicable. Analyses will be stratified by BMI ( $< 30 \text{ kg/m}^2$  vs.  $\geq 30 \text{ kg/m}^2$ ), age (18-49, 50-64,  $\geq 65$  years), sex assigned at birth (female, male) and race and ethnicity, and country, if sample sizes allow, at initiation of CAB+RPV LA regimen. Factors associated with CVF will be assessed using a logistic regression model. The number and proportion of participants with history of resistance to INSTI or NNRTI classes and INSTI and/or NNRTI RAMs at discontinuation/CVF with

results will be described. Subsequent regimen after discontinuation/CVF and virologic outcomes will be assessed. Participant surveys will be summarized descriptively for item and summary score (where applicable). The WHOQOL-HIV BREF, HIVTSQs, and HIVTSQc will be scored according to instrument scoring guidelines and derived scores will be summarized descriptively. All analyses will be performed on the observed data only and no missing values will be imputed.

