## 6. RESEARCH QUESTION AND OBJECTIVE(S)

### 6.1. Primary Objective

The overall objective of this global study is to describe participant characteristics and assess clinical outcomes and patient-reported outcomes among people with HIV who receive CAB+RPV LA regimen.

1. To describe baseline demographics, clinical characteristics and patterns of use among participants receiving CAB+RPV LA
  - Descriptive analysis of study population by baseline demographic and clinical characteristics
  - Monitor for use of OOLI
2. To assess the persistence, discontinuation, and adherence among participants receiving CAB+RPV LA
  - Persistence: Proportion of participants still on CAB+RPV LA at time of analysis, after 6, 12, and 24 months of use and at study end
  - Proportion of participants discontinuing the regimens of interest will be assessed
    - a. Reasons for discontinuation will be assessed

- Non-adherence to the dosing schedule will be assessed by:
  - a. Estimating the number of participants who missed 1 or more consecutive injections without taking daily oral bridging therapy or any other oral ARV regimen while not on CAB+RPV LA and estimating the mean and median number of injections missed during a 12-month period
  - b. Estimating the number of participants who received the injections more than 7 days earlier or later than their scheduled injection visit and median time from target injection to actual injection date of early delayed injections
  - c. Estimating the number of participants who missed 1 or more consecutive injections without taking daily oral bridging therapy or those who received the injections more than 7 days earlier or later than their scheduled injection visit (combined group A or B) and describe individual characteristics for the participants who are non-adherent.
  
- 3. To assess virologic effectiveness (i.e., proportion of participants experiencing virologic suppression and CVF) among participants receiving CAB+RPV LA regimen
  - Estimate overall number and proportion of participants with CVF and time to CVF (months)
  - Estimate the proportion of participants with CVF during the first 6 months after initiation of CAB+RPV LA
  - Estimate the proportion of participants with CVF 6, 12, and 24 months after initiation of CAB+RPV LA
  - Assessment of virologic suppression among participants on CAB+RPV LA regimen during first 6 months and at 6, 12, and 24 months after initiation of the regimen

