  - Assessment of number and proportion of participants who remain suppressed (VL <50 c/mL) throughout all follow-up and at last follow-up
  
- 4. To assess factors associated with CVF among participants receiving CAB+RPV LA regimen

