### Prospective Participants:

[figure not shown]
Prospective participants will include individuals enrolled from November 2025 until study size is reached. Participants will be enrolled prior to their first CAB+RPV LA injection, either during the optional oral lead-in (OOLI) phase, if applicable, or directly before their first CAB+RPV LA injection for those on the direct-to-injection (DTI) pathway. The baseline survey will be administered before the first CAB+RPV LA injection. The participants will be followed for a minimum of two years, unless they withdraw from the study, are lost to follow-up, or pass away. Participants who discontinue and switch to a subsequent regimen or who experience CVF will be followed-up for a minimum of 6 months and may be extended until viral load assessment is completed, with a maximum duration of 12 months.

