#### 7.5. Study Size

The study will aim to enroll up to approximately 2,000 participants. Among them, it is estimated that 250 participants are already receiving CAB+RPV LA at the time of study start, and 1,750 participants will be newly initiating CAB+RPV LA.

There is no formal statistical hypothesis to be tested in these analyses. The study will be descriptive in nature and will focus on absolute effectiveness estimation. A precision calculation was performed using power analysis and sample size (PASS) software version 14 using the exact Clopper-Pearson method based on the cumulative probabilities of the binomial distribution for 1 proportion.

In order to demonstrate the estimated precision for the total sample size and also among the groups of participants already receiving and newly initiating CAB+RPV LA, Table 1 presents the precision calculations for the width of 95% confidence intervals for a range of proportions and a combination of sample sizes. It is anticipated that data from 2,000

participants are thought adequate to provide reasonable precision around a point estimate (here defined as a proportion) to meet the study objectives. With 2,000 participants, the 2-sided 95% confidence interval precision width for the estimation of virologic failure rate will range from 1.28% and 2.13% for a failure rate ranging from 2% to 6%.

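### The model for factors associated with CVF is a logistic regression with no time horizon, person-time offset or censoring rule, although follow-up is unequal by design

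*Protocol*

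**What the plan says.** Protocol section 6.1 makes this a primary objective: "To assess factors associated with CVF among participants receiving CAB+RPV LA regimen". The synopsis (Data Analysis) names the method: "Factors associated with CVF will be assessed using a logistic regression model". Section 7.7.1.1 repeats it with an open list, "factors such as, age, sex assigned at birth, race, geographic region, BMI, injection drug use (IDU), CD4 count, history of AIDS-defining events", followed by "core class in prior regimen and comorbidities associated with CVF will be explored using a logistic regression model". Neither place ties the model to a timepoint or says how participants with incomplete follow-up enter it.

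Follow-up is set out in section 7.2:

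- Prospective participants: "The participants will be followed for a minimum of two years", except on withdrawal, loss or death. No maximum is given, and section 6.2 provides for analysis of data beyond two years.
- Retrospective participants: up to two years.
- After a switch or CVF: at least 6 months, which "may be extended until viral load assessment is completed, with a maximum duration of 12 months".

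Section 7.7.1.1 accounts for person-time in event rates, but through unadjusted Poisson regression. Methods for right-censoring may be considered for selected outcomes, with time to discontinuation as the example. Section 7.7.1.3 plans no sensitivity analyses.

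Section 7.5 sizes the study on the precision of a single proportion, "for a failure rate ranging from 2% to 6" (per cent), at N = 2,000. It does not size the regression.

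**The concern.** Logistic regression compares the odds of CVF ever being recorded. When participants are observed for different lengths of time, those odds reflect both the rate of failure and the time available to observe it. A covariate related to observation time picks up the second component. Several listed factors could be related to it. Region could, if countries start enrolling at different times or lose participants at different rates. So could anything that drives discontinuation, since a switch shortens follow-up.

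This is the only covariate model for CVF that the plan names, and it serves a primary objective. With no sensitivity analysis planned, nothing would show whether a reported risk factor, or an apparently protective one, reflected follow-up length. A second, lesser issue is the small number of events relative to the list of factors.

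**Working it through.** **1. The plan's own figure.** Clopper-Pearson limits, with x = N × p, are L = Beta(0.025; x, N−x+1) and U = Beta(0.975; x+1, N−x). At N = 2,000:

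- p = 0.02, x = 40: 0.0143 to 0.0271, width 0.0128.
- p = 0.06, x = 120: 0.0500 to 0.0713, width 0.0213.

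Both widths match section 7.5 and Table 1. The plan therefore implies 40 to 120 CVFs at full enrolment.

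**2. A null factor related to follow-up length.** Assume a constant CVF hazard h, the same at both levels of the factor, and reference follow-up of 24 months. With 2% CVF by month 24, h = −ln(0.98)/24 = 0.000842 per month. Risk by month m is p(m) = 1 − exp(−h·m), and OR = [p(m)/(1−p(m))] / [0.02/0.98].

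Worked case, m = 12: p = 0.01005, odds 0.01015, reference odds 0.02041, OR = 0.50.

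| Follow-up compared (months) | OR at 2% CVF | OR at 6% CVF | Rate ratio |
|---|---|---|---|
| 12 vs 24 | 0.50 | 0.49 | 1.00 |
| 18 vs 24 | 0.75 | 0.74 | 1.00 |
| 36 vs 24 | 1.51 | 1.52 | 1.00 |

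These rows assume that everyone at one level has the shorter or longer follow-up. They show how the odds ratio tracks time and do not forecast this study.

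**3. A null factor that only raises discontinuation.** The protocol gives no discontinuation rate. Assume that a proportion q discontinues by month 24 in the reference group, so d = −ln(1−q)/24, and that the factor multiplies d by k. If follow-up continues e months past discontinuation, up to month 24, mean follow-up is M = e + [1 − exp(−d(24−e))]/d. Applying the hazard from step 2 to each group's mean follow-up gives the odds ratio. For q = 25%, k = 3, e = 0, the means are 20.86 and 16.08 months and OR = 0.77.

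| q, k | Follow-up stops at discontinuation | 6 months more | 12 months more |
|---|---|---|---|
| 15%, 2 | 0.92 | 0.96 | 0.98 |
| 15%, 3 | 0.86 | 0.92 | 0.96 |
| 25%, 2 | 0.87 | 0.93 | 0.97 |
| 25%, 3 | 0.77 | 0.87 | 0.94 |

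The last two columns use the 6 to 12 months in section 7.2 and count CVF in that period at the same hazard.

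**4. Events against parameters.** Section 7.7.1.1 names ten factors.

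- One parameter each: 40/10 = 4.0 and 120/10 = 12.0 events per parameter.
- With the protocol's categories for age (3 levels), BMI (3) and CD4 (5), those three take 2 + 2 + 4 = 8. The other seven at one each bring the total to 15, giving 40/15 = 2.7 and 120/15 = 8.0.

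A simulation (N = 2,000, 500 data sets per setting, assumed category shares) counted fits with at least one divergent coefficient, defined as an absolute log OR above 8:

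| Parameters (assumed) | about 40 events | about 80 | about 120 |
|---|---|---|---|
| 10 | 14% | 2% | 0% |
| 20 | 88% | 54% | 31% |

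For a common binary factor (25% prevalence, true OR 2), the mean log OR stayed within about 4% of the truth in every setting.

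**The case against.** The strongest reply concerns the estimand. If CVF counts only while on CAB+RPV LA, discontinuation is a competing event. Without other censoring, the Aalen-Johansen cumulative incidence then equals the simple proportion. The 0.77 to 0.92 in step 3 would be a real difference in risk, not bias. This stands for that case. It does not cover follow-up that differs by region, cohort, withdrawal or loss, and the plan does not say which case applies.

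A fixed horizon is also available. Section 7.3.2 defines CVF by an assessment timepoint, and section 6.1 plans to "Estimate the proportion of participants with CVF 6, 12, and 24 months after initiation of CAB+RPV LA". But neither statement of the logistic model adopts such a horizon, and those who leave before it would still need handling.

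Four stronger readings are tempting and are not supported:

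- *Leavers are counted as CVF-free for the full period.* The protocol does not say so. The synopsis limits analyses to observed data. The rule is simply not given.
- *The odds ratios will be biased or infinite.* Follow-up bias requires a factor related to follow-up length. Divergence affects rare categories; common factors are imprecise but close to unbiased.
- *The model has about 20 parameters.* The list is open, the coding is not fixed, and the text does not say that all factors enter one model. Counts from 10 to 41 fit it. Coding, selection and penalisation may properly sit in an SAP that is not at hand.
- *The cap after CVF distorts the analysis.* It cannot affect first CVF, which has already occurred.

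Finally, the study is descriptive with no formal hypothesis, which limits the consequences but leaves the objective primary.

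**Conclusion.** The point holds as a choice of method. The plan fixes a model without time for a primary objective, while its own design makes observation time unequal and its own rates allow for that.

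The size depends on how strongly a factor is related to follow-up. It is large where whole groups differ in follow-up length (OR 0.50 to 1.51 in step 2). It is modest where the factor acts only through discontinuation: 0.77 to 0.92 if follow-up stops there, 0.87 to 0.98 with the further 6 to 12 months. These figures assume a constant hazard, the stated discontinuation rates and no true effect of the factor.

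Sparse data are a secondary risk to flag. At 2% CVF there are about 4 events per parameter with the leanest coding and fewer with the protocol's categories. The count falls below 40 events if enrolment falls short of 2,000 at that rate.

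**What to change.** In the synopsis (Data Analysis) and section 7.7.1.1, replace the logistic model for CVF factors with one of:

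- Poisson regression with a log person-time offset, the scale already used for rates; or
- a cause-specific Cox model.

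Censor at end of follow-up, and state whether CVF after discontinuation counts. If a risk at 6, 12 or 24 months is wanted, name the horizon and use a censoring-aware estimator. Both models still assume that, given the covariates, censoring is unrelated to CVF.

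For the sparse-data risk, use Firth penalisation or a short pre-ranked list of factors, in the protocol or the SAP.

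The cost is wording; the data collected do not change. A rate or hazard ratio replaces the odds ratio, and with a short list fewer factors enter the adjusted model.

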#### **7.7.1.2. Data handling conventions**

Data handling conventions applicable to this study design as described in the Guidelines for Good Pharmacoepidemiology Practices (GPP) issued by the International Society for Pharmacoepidemiology (ISPE) will be followed to ensure ethical and scientific recording and reporting of non-interventional trials that involve data from human subjects. The following procedures will be undertaken:

- Automatic checks and prompts are built into the EDC program (e.g., checks for out-of-range numeric values). Each individual eCRF will be further evaluated for logical consistency between study variables, potential outliers, and missing information.
- Inconsistencies noted in the eCRF data will be queried with the site using data-clarification procedures. Sites will be queried for clarification via the EDC system if any such issues are identified. Database lock will be issued when all queries have been resolved.
- Participant medical chart data will be abstracted into the eCRF by qualified site staff, identified only by the unique subject identification number. Linkage between the identification number and the participant records will be recorded at a site-level only and will not be shared externally with RTI-HS or ViiV Healthcare. Data will be abstracted by site staff from participant medical records and entered into an eCRF hosted on the secure EDC system. The link between the subject identification code and the individual participant must be destroyed by the site at the end of the study.

### **7.7.1.3. Sensitivity analyses**

No sensitivity analyses are planned.

### **7.7.2. Secondary Analysis/Exploratory Analysis**

Individual surveys will be summarized descriptively for item and summary score (where applicable). The WHOQOL-HIV BREF, HIVTSQs, and the HIVTSQc will be scored according to instrument scoring guidelines. All analyses will be performed on the observed data only, and no missing values will be imputed.

## **7.8. Quality Control and Quality Assurance**

This project will be conducted in accordance with all applicable regulatory requirements. The Office of Quality Assurance, an independent unit that reports to the vice president of RTI-HS, will oversee quality assurance for this study.

Standard operating procedures will be used to guide the conduct of the study. These procedures include rules for secure and confidential data storage, methods to maintain and archive project documents, quality control procedures for programming, standards for writing analysis plans, and requirements for senior scientific review.

All programming written by one study analyst will be independently reviewed by a different analyst, with oversight by a senior statistician.

All key study documents, such as the analysis plan, data collection forms, and study reports, will undergo quality control review, senior scientific review, and editorial review.

### **7.8.1. Site Training**

Investigators and study coordinators will be trained via an initial web-based training session on the protocol, including adverse event (AE) reporting, study flow, EDC system, documentation, site responsibilities and expectations, and any applicable study processes. Any new information relevant to the performance of this study will be forwarded to the medical staff during the study.

No on-site monitoring visits will be performed for this study unless there is a specific need to meet with the site team. Remote data monitoring will be conducted during the life of the study to ensure linkage and integrity between the eCRFs and the participant surveys and to identify missing or unclear data in the eCRFs and issue queries.

RTI-HS will closely monitor the participant recruitment and data collection on a regular basis. Specifically, RTI-HS will provide oversight of activities, including screening participants, recruiting and obtaining consent from participants, and completion of electronic surveys and eCRFs. RTI-HS will maintain regular communication with all sites and will assess progress and site performance and address any issues as they arise.

## **7.9. Limitations of the Research Methods**

Limitations of this study are common to non-randomized non-interventional study. This is a study of routine clinical care and reflects treatment practice across multiple countries and diverse clinical sites. This will be a single treatment group analysis with no formal statistical comparisons. While the study aims to include approximately 2,000 users of the CAB+RPV LA regimen, market uptake of the regimen and participants willingness to participate will dictate timelines for enrollment and data collection. The results from this study should be interpreted cautiously, with careful consideration given to the limitations of the observational study design.

### **7.9.1. Study Closure/Uninterpretability of Results**

Not applicable; these are descriptive analyses of observational, real-world data.

## **7.10. Other Aspects**

None

## **8. PROTECTION OF HUMAN SUBJECTS**

### **8.1. Ethical Approval and Subject Consent**

The study will be conducted in accordance with legal and regulatory requirements; with scientific purpose, value, and rigor; and will follow generally accepted research practices described in GPP issued by Public Policy Committee of the ISPE.

Ethics review requirements and processes for prospective studies vary among countries and are governed by local standards. This study will be conducted in accordance with such standards in each country.

RTI-HS, with assistance from local clinical research associates, will work in collaboration with the site Principal Investigators to submit the necessary ethics review applications in each country at both the site and the national or regional levels, as well as notify/register the local Health Authority, as and where applicable.

Informed consent will be obtained from participants (or their legally acceptable representative) by site study staff before data collection. The person obtaining consent will be responsible for ensuring that each participant fully understands the nature, purpose, risks, and benefits associated with participation. Each participants will be provided with a copy of his or her signed informed consent form. The investigator, or a person designated by the investigator, will retain the original of each participant's signed consent form.

Participants (or the participant's legally acceptable representative) may choose to withdraw consent at any time. At time of withdrawal, all data that have already been processed and analyzed will be kept to guarantee the integrity of the study. Once data has been processed and analyzed (i.e., at the point of data analysis), the information may continue to used.

